CLINICAL STUDY PROTOCOL

A randomized controlled trial comparing bp-MRI and mp-MRI on the screening accuracy for clinically significant prostate cancer before MRI-fusion targeted biopsy

VERSION NO.3

DATES (20240429)

INVESTIGATORS

[name]

SITES

Chang Gung Memorial Hospital at Linkou

Table of Contents

Section	Page
1. Synopsis.....	1
2. Introduction and Rationale.....	7
3. Objectives and Endpoints	9
3.1. Study Objectives	9
3.2. Study endpoints	9
4. Study Design.....	10
4.1. Overall Design (Flow Chart)	11
4.2. Number of Patients.....	11
4.3. Schedule of Activities (Time-Event scheme)	12
5. Study Population.....	13
5.1. Inclusion Criteria.....	13
5.2. Exclusion Criteria	13
5.3. Withdrawal criteria	13
6. Treatments	13
6.1. Treatments Administration	13
6.2. Concomitant Therapy	13
7. Efficacy Assessments	13
8. Safety Assessments	
9. Adverse Event reporting	
9.1. Definition and reports of Adverse Events.....	14
9.2. Adverse event follow-up	14
10. Criteria for the termination of the trials	
11. Statistical Considerations	
11.1. Sample Size Determination	15
11.2. Planned Statistical methods of analysis.....	16
11.2.1. Efficacy analyses.....	16
11.2.2. Safety analyses	16
11.2.3. Additional analyses	16
11.2.4. The level of significance	16
11.2.5. Analysis Population.....	16
12. Direct access to source data/documents	
13. Ethical considerations	
14. Data handling and keeping	
15. Financing and Insurance	
16. References.....	17

1. Synopsis

Protocol Title : A randomized controlled trial comparing bp-MRI and mp-MRI on the screening accuracy for clinically significant prostate cancer before MRI-fusion targeted biopsy.

Study Objectives : We aim to address these questions for Taiwan males suspicious of csPCA, with PSA range of 4-20 ng/ml by conducting a RCT trial.

Investigational product(s) : Magnetic Resonance Imaging (MRI)

Development Phase : I II III IV 其它 _____ 不適用

Study Design :

1. Experimental Group

Control Group : Placebo
 Study Drug (Name、Dose、Usage) _____
 Other _____

2. Blinding : Open Evaluator-blind Single-blind(patient) Double-blind(patient+PI)
 Double Dummy Other _____

3. Randomization: Yes No

4. Parallel design Crossover design Other _____ Not applicable

5. Treatment Period : _____ (days/weeks/months/years) Not applicable

6. Study Period: _____ years (or From 01/02/2024 to 31/01/2026)

6. Dose adjustment : Mandatory Selectively No Not applicable

7. Study location : Single Multi-center Global

Endpoints (Outcome measure) :

1. Primary endpoint:

The proportion of men with clinically significant Prostate cancer(csPCA), defined as a diagnosis of ISUP (International Society of Urogenital Pathology) Grade group ≥ 2 prostate cancer, in at least one biopsy core.

2. Secondary endpoints:

1. The proportion of men with a diagnosis of any PCA
2. The proportion of men with a diagnosis of clinically insignificant PCA, defined as ISUP grade group 1 PCA (ISUP 1 PCA)
3. The proportion of men with a diagnosis of csPCA
 - Only in targeted biopsy
 - Only in systematic biopsy
4. The proportion of csPCA of all suspicious lesions from bp-MRI and mp-MRI.

3. Exploratory endpoints (if any):

nil

Inclusion/Exclusion Criteria :**Inclusion criteria (All of the followings)**

1. Men \geq 50 years of age
2. Clinical suspicion of prostate cancer and indicated for prostate biopsy
3. Serum Prostate-specific antigen (PSA) between 4~20 ng/mL
4. Eligible for MRI study
5. Digital rectal examination \leq cT2 (organ-confined cancer)
6. Able to provide written informed consent.

Exclusion criteria: (any of the followings)

1. Prior prostate biopsy in the 6 months before screening visit
2. Prior diagnosis of prostate cancer
3. Contraindicated to prostate biopsy: active urinary tract infection, failed insertion of transrectal ultrasound probe into rectum (abdominal perineal resection, anal stenosis), uncorrectable coagulopathy, antiplatelet or anticoagulant which cannot be stopped (continue low-dose aspirin before and after biopsy is permitted)
4. Contraindicated to MRI study: contrast medium allergy, claustrophobia, or other contraindications (e.g.: intra-abdominal metal foreign bodies).
5. Patients without histological results of prostate biopsies due to patient refusal for biopsy or loss of follow up before biopsy being done
6. Patients have prior treatments for prostate cancers or any kinds of hormone therapy, immunotherapy, chemotherapy, radiation therapy of the pelvic cavity.
7. Patients' withdrawal of informed consents of this study

Withdrawal criteria

1. Patients could not complete the scheduled MRI examinations
2. MRI images of insufficient quality to localized csPCA or to exclude the presence of csPCA

Study Procedures :**Feasibility in recruiting adequate patients for this trial**

There are estimated 600+ patients diagnosed and treated as prostate cancer in our institute every year. We performed about 800+ prostate biopsies in our hospital per year. Assuming 40-50% of men agree recruitment to this study, about 200-250 men will be recruited per year, and the recruitment for the whole study should complete in 24 months, and the study to complete in 30 months.

Study intervention**MRI prostate**

Bi-parametric and multi-parametric MRI prostates can be performed using a 3.0 Tesla scanner with a pelvic phased array coil with or without contrast. MRI findings will be reported according to PI-RADS (Prostate Imaging-Reporting and Data Systems) v2.1 recommendations. (12) MRI will be reported by radiologists with experience in MRI prostate reporting. PI-RADS scores 3-5 will be regarded as suspicious, and targeted plus systematic biopsy will be performed.

Prostate biopsy

In patients with suspicious lesion found on MRI (identified as PI-RADS score 3-5 lesions on bp-MRI or mp-MRI), biopsies will be done via trans-perineal approach under general anesthesia with 3 cores of targeted biopsy from each lesion, alone with 3 cores of systemic biopsy from right and left

lobes respectively.

[figure not shown]
In those without identified suspicious lesions on MRI, a standard 12-core systematic biopsy will be performed via trans-rectal approach under local anesthesia.

All biopsies will be performed by Urologists experienced in both targeted and systemic prostate biopsy. Targeted biopsies will be done by software-assisted MRI-USG fusion registration. Peri-biopsy antibiotics are given according to our clinical guidelines.

Post-biopsy management

Patients will be discharged after prostate biopsy when they can pass urine without significant gross hematuria, and clinically stable. They will be followed up in the clinic within 10 days after a biopsy to review pathology results and complications. All biopsies will be assessed by experienced Urogenital pathologists and reported according to the International Society of Urological Pathology (ISUP) consensus. (23) The study period ends after the first clinic follow-up.

Figure 1. Study design

Concomitant Treatments : 不適用

1. Concomitant Therapy :
2. Prohibited Therapy :

Statistical Methods :

1. Main study Hypothesis : Equality Superiority Non-inferiority
 Equivalence Other _____
2. Estimated Sample Size : 整個試驗預計納入人數 370，整個試驗可評估人數 370
 本中心預計納入人數 370，本中心可評估人數 370
3. Efficacy assessment group : Intent-to-treat (ITT) Per-Protocol (PP)
 Other _____
 附註：意圖治療：Intent-to-treat (ITT)；依計畫書：Per-Protocol (PP)
4. Interim analysis : Yes No

Statistical methods :

The primary objective of this study is to evaluate the csPCa detection in bp-MRI arm versus mp-MRI arm. We hypothesise that bp-MRI is non-inferior to mp-MRI in detecting

csPCa. The baseline characteristics of the two groups will be compared. Continuous variables will be evaluated using the student's t-test and the Mann-Whitney U test. In contrast, categorical variables will be analysed using the Chi-squared and Fisher's exact tests, as applicable. The effect size and 95% CI will be presented for secondary outcomes, and a 2-sided p-value less than 0.05 will be considered statistically significant. All statistical analyses will be performed using SPSS v.24.0 (IBM Corp., Armonk, NY, USA).

5. Handling of Missing Data :

Analysis would be carried on for available data after exclusion of the missing data.

2. Introduction and Rationale

Prostate cancer (PCa) is the second most commonly diagnosed cancer and the fifth leading cause of cancer death in males worldwide [1]. It is traditionally less prevalent in Asia but the incidence has increased in the past decades [2-4]. According to the data released by Taiwan Health Promotion Administration, Ministry of Health and Welfare Cancer Statistics, Prostate cancer is now the fifth most common male cancer in Taiwan [5].

Prostate-specific antigen (PSA) is a widely used test for prostate cancer detection. However, PSA is highly sensitive but not very specific [6]. Elevated PSA levels typically lead to referrals to urologists for further evaluation, including magnetic resonance imaging (MRI) and potentially a prostate biopsy. Biopsies carry a risk of complications, with infections at the biopsy site being a major concern, leading to sepsis in 2–5% of cases [7]. Concerns about missing clinically significant cancer, unnecessary biopsies, and overtreatment of low-risk disease have driven the search for improved biopsy methods that are both more accurate in detecting cancer and safer for patients.

The application of Magnetic Resonance Imaging (MRI) in identifying potentially cancerous lesions within the prostate gland dates back to the 1980s [8, 9]. A significant leap forward occurred in the 1990s with the introduction of dynamic contrast-enhanced (DCE) and diffusion-weighted imaging (DWI) MRI protocols [10, 11]. With the introduction of MRI of the prostate and the improvement in PCa detection and localization, an alternative procedure, known as MRI-targeted biopsy (MRI-TB), has been shown to have comparable or even higher detection rates of csPCa compared to TRUS-system biopsy (SB). Targeted prostate biopsies from MRI-suspicious lesions have improved the cancer detection rate (CDR) of csPCa compared with systematic TRUS-guided biopsies. The implementation of pre-biopsy multiparametric MRI has effectively reduced the risk of both underdiagnosis of clinically significant disease and overdiagnosis of clinically insignificant disease, which were previously associated with random prostate sampling. (19)

Two types of MRIs have emerged for diagnosing PCa: Bi-parametric MRI (bpMRI), which combines T2-weighted images with DWI, and multi-parametric MRI (mpMRI), which incorporates DCE with or without spectroscopy, into its imaging protocol [12]. The determination of PCa utilizing mpMRI relies on the Prostate Imaging Reporting and Data System (PI-RADS) score based on PI-RADS versions 2.1 recommendation; however, if DCE is of insufficient quality or not available, an alternative PIRADS scores based on mp MRI could be evaluated using modified score rules provided by PRIRADS v 2.1 as well [13].

In 2015, Rais-Bahrami et al. employed mpMRI with the exclusion of DCE results to analyze

Protocol: BMPFB Trial

biopsy outcomes of individuals. Their research explored the application of bpMRI in diagnosing PCa. They found the bpMRI with PCa detection overall accuracy of 80% [14]. Bass et. al. conducted a meta-analysis across 44 cohort studies, revealing that the sensitivity, specificity, and AUC of bpMRI for csPCa were 87%, 72%, and 87%, respectively [15]. Furthermore, several studies have demonstrated that both bpMRI and mpMRI exhibit comparable diagnostic effectiveness in detecting PCa and csPCa. The overall sensitivity and specificity for mpMRI were 76% and 89%, while bpMRI achieved 74% sensitivity and 90% specificity [16]. For patients with varying total prostate-specific antigen (tPSA) levels, both mpMRI and bpMRI exhibit identical accuracy in detecting PCa or csPCa. However, Pan et al. found that mpMRI detected more cases of PCa and csPCa in the tPSA range of 10–20 ng/ml. In contrast, for other tPSA ranges (tPSA < 4 ng/ml, 4–10 ng/ml, 20–100 ng/ml), the detection rates of PCa and csPCa were similar between bpMRI and mpMRI [17]. Collectively, bpMRI proves to be an effective tool for PCa screening and diagnosis, with comparable diagnostic accuracy to mpMRI. Additionally, when omitting the DCE protocol from the MRI, patients experience reduced costs and shorter imaging times, while healthcare providers can offer more tests to their patient population.

Although these retrospective studies and some meta-analysis shows similar sensitivity and specificity for detecting csPCA in Europe and US patients, there is still a lack of randomized control trials validating the non-inferiority of bpMRI as compared with mpMRI for detecting and guiding targeted biopsies of csPCA in patients of PSA 4-20 ng/ml in the world and Taiwan. Thus, we aim to address this questions for Taiwan males suspicious of csPCA, with PSA range of 4-20 ng/ml by conducting a RCT trial.

2.1 Investigational product(s)

Not Applicable

2.2 Animal and preclinical study data

Not Applicable

2.3 Clinical data

Not Applicable

2.4 Risks / benefits Assessment

MRI (Magnetic Resonance Imaging) is a commonly used medical imaging technology, primarily for detailed observation of internal body structures and functions. Its risks are relatively low, but there are still some considerations, while its potential benefits are quite significant.

Risks:

- For patients with cardiac pacemakers, metal implants, or certain types of metal fragments, MRI can pose risks.
- The high-intensity magnetic field may affect or move metal objects inside the body.
- In very rare cases, the use of contrast agents may cause mild to severe allergic reactions.

Potential Benefits:

- MRI does not use ionizing radiation, resulting in less exposure to radiation for patients compared to X-rays or CT scans.
- It provides extremely detailed images of soft tissues, which helps in diagnosing various diseases such as brain and spinal cord lesions, musculoskeletal injuries, heart diseases, and cancer.

Protocol: BMPFB Trial

- MRI is very useful for long-term tracking and assessing the progression of certain medical conditions.

2.5 Regulatory

This study will be conducted in compliance with the protocol approved by the Institutional Review Board, and according to Good Clinical Practice standards. No deviation from the protocol will be implemented without the prior review and approval of the IRB except where it may be necessary to eliminate an immediate hazard to a research subject. In such case, the deviation will be reported to the IRB as soon as possible.

Subject data confidentiality is maintained through the use of identification numbers to protect the privacy of participants. It ensures that no information about the participants' involvement in the study or their personal information is disclosed. Regarding the results and diagnoses from participant interviews, the research leader will maintain a confidential stance, carefully safeguarding their privacy.

3. Objectives and Endpoints

3.1 Study Objectives:

3.1.1 Primary objective:

We aim to address these questions for Taiwan males suspicious of csPCA, with PSA range of 4-20 ng/ml by conducting a RCT trial.

3.2 Study endpoints:

3.2.1 Primary endpoint:

The proportion of men with clinically significant Prostate cancer(csPCA), defined as a diagnosis of ISUP (International Society of Urogenital Pathology) Grade group ≥ 2 prostate cancer, in at least one biopsy core.

3.2.2 Secondary endpoints:

1. The proportion of men with a diagnosis of any PCA
2. The proportion of men with a diagnosis of clinically insignificant PCA, defined as ISUP grade group 1 PCA (ISUP 1 PCA)
3. The proportion of men with a diagnosis of csPCA
4. Only in targeted biopsy
5. Only in systematic biopsy
6. The proportion of csPCA of all suspicious lesions from bp-MRI and mp-MRI.

4. Study Design

We propose to conduct a phase III randomised controlled trial to evaluate the detection of clinically significant prostate cancer (csPCA) by bp-MRI versus mp-MRI before MRI-fusion targeted biopsy. Clinically significant prostate cancer (csPCA) is defined as ISUP (International Society of Urogenital Pathology) Grade group ≥ 2 prostate cancer.

Patients who are suspicious of prostate cancers with abnormal digital examination, or abnormal ultrasound and having a pre-MRI and were scheduled to receive prostate biopsy will be enrolled in this study. Patients will be randomized in a 1:1 manner to bp-MRI and mp-MRI. Patients with clinical suspicion of prostate cancer on MRI with PI-RADS (Prostate Imaging-Reporting and Data System, version 2.1) [18] score 3-5 will be arranged to receive MRI-Ultrasound fusion biopsy for targeted and systemic biopsy. Patients who have no suspicious lesions found on MRI will receive standard

Protocol: BMPFB Trial

systemic biopsy only instead. The study flowchart is provided in Figure 1. The detection rates of csPCa will be compared between arms. The study hypothesis is that bp-MRI has similar detection rate for csPCa comparing to mp-MRI.

To formulate the randomization codes and distribution process, we first plan to recruit a total of 370 participants. Then, we choose a block size of 4 to maintain balance between groups while reducing the predictability of the assignment sequence. Utilizing the block randomization method, we generate random codes for each block to ensure an equal number of participants in each treatment group. Subsequently, a complete table of random codes is created using a random number generator, serving as the basis for participant assignment.

As participants enter the study, they will be assigned to the respective groups according to the sequence of the random code table, namely the bp-MRI group or the mp-MRI group. This process not only ensures the randomness of the assignments but also helps maintain the fairness and transparency of the research. After each assignment, we record the detailed information of the participants and the group they are assigned to, ensuring the traceability and transparency of the entire process.

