4.1 Overall Design

Study intervention

MRI prostate

Bi-parametric and multi-parametric MRI prostates can be performed using a 3.0 Tesla scanner with a pelvic phased array coil with or without contrast. MRI findings will be reported according to PI-RADS (Prostate Imaging-Reporting and Data Systems) v2.1 recommendations. (12) MRI will be reported by radiologists with experience in MRI prostate reporting. PI-RADS scores 3-5 will be regarded as suspicious, and targeted plus systematic biopsy will be performed.

Prostate biopsy

In patients with suspicious lesion found on MRI (identified as PI-RADS score 3-5 lesions on bp-MRI or mp-MRI), biopsies will be done via trans-perineal approach under general anesthesia with 3 cores of targeted biopsy from each lesion, alone with 3 cores of systemic biopsy from right and left lobes respectively.

In those without identified suspicious lesions on MRI, a standard 12-core systematic biopsy will be performed via trans-rectal approach under local anesthesia.

All biopsies will be performed by Urologists experienced in both targeted and systemic prostate biopsy. Targeted biopsies will be done by software-assisted MRI-USG fusion registration. Peri-biopsy antibiotics are given according to our clinical guidelines.

Post-biopsy management

Patients will be discharged after prostate biopsy when they can pass urine without significant gross hematuria, and clinically stable. They will be followed up in the clinic within 10 days after a biopsy to review pathology results and complications. All biopsies will be assessed by experienced Urogenital pathologists and reported according to the International Society of Urological Pathology (ISUP) consensus. (23) The study period ends after the first clinic follow-up.

[figure not shown]
In our medical research, we prioritize protecting participant privacy and confidentiality. We use unique research codes to anonymize personal details like names and IDs. The principal investigator keeps consultation results and diagnoses confidential, even in published research. Participants consent to have their records reviewed by authorized parties for legal and ethical compliance, with a promise of maintaining their anonymity. For safety, we may inform

participants' other doctors about their trial involvement to manage treatment interactions.

Overall, these steps ensure participant privacy and safety throughout the research.

Flow Chart (試驗流程圖) :

Figure 1. Study design

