11.2.1 Efficacy analysis

Not applicable

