11.3 Analysis Population

Not applicable

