11.4 Procedure for accounting for missing, unused and spurious data

The incomplete clinical data and sequencing data with poor quality will be excluded in the study.

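### Does the targeted-core csPCa endpoint need a stated denominator before men with a negative MRI can be handled correctly?

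*Combined protocol and SAP*

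**What the plan says.** Section 3.2.2 and the synopsis list, among the secondary endpoints, csPCa "Only in targeted biopsy" and a companion line for systematic biopsy. In the synopsis both are sub-items of the proportion of men diagnosed with csPCa. In 3.2.2 the same lines carry their own numbers. The last secondary endpoint is per lesion: "The proportion of csPCA of all suspicious lesions from bp-MRI and mp-MRI".

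Section 4.1 gives targeted plus systematic cores to men with PI-RADS 3-5. For the others: "In those without identified suspicious lesions on MRI, a standard 12-core systematic biopsy will be performed via trans-rectal approach under local anesthesia".

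On missing data the synopsis says "Analysis would be carried on for available data after exclusion of the missing data", and section 11.4 says "The incomplete clinical data and sequencing data with poor quality will be excluded in the study". The headings "11.2.1 Efficacy analysis" and "11.3 Analysis Population" are both marked as not applicable. Section 11.2 promises an effect size and 95% CI for secondary outcomes.

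**The concern.** A man with a negative MRI has no targeted cores by design. If he counts as not detected, the endpoint is MRI-guided detection per randomised man, and randomisation protects the comparison. If an analyst treats his missing targeted result as missing data and drops him, the endpoint becomes the positive predictive value of an MRI call. That would compare subsets chosen after randomisation by the test under study. An arm that calls fewer men positive could then look better while finding fewer cancers by targeting.

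This matters because the Introduction's rationale includes guiding targeted biopsies, and this is the per-man result that isolates that role. The any-core primary endpoint also counts cancers found in systematic cores.

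Two smaller points go with it. The word for exclusivity in the endpoint could mean csPCa in targeted cores whatever the systematic cores show, or in targeted cores and nowhere else. And the title speaks of screening accuracy, although no endpoint is an accuracy measure.

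**Working it through.** The plan gives no figure for this endpoint, so there is none to reproduce. The power statement in section 11.1 concerns the primary endpoint and is not used here; only its 148 evaluable men per arm is taken over. (Its 80.145% does not come back from its stated inputs, which give 48.2%. That is a separate matter.)

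**Inputs**
- Accuracy, from the Introduction: "The overall sensitivity and specificity for mpMRI were 76% and 89%, while bpMRI achieved 74% sensitivity and 90% specificity". These are overall figures; applying them to csPCa is an assumption.
- Prevalence D = 0.28. Section 11.1 gives this as the mp-MRI detection proportion; using it as prevalence is an assumption. D = 0.40 is shown as a second value.
- Every MRI-positive cancer is hit by targeting. A common hit rate below 1 scales both differences and leaves their signs unchanged.

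**Formulas**
- All men: sens × D
- MRI-positive share: sens × D + (1 − spec) × (1 − D)
- MRI-positive men only: the first divided by the second

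**Results at D = 0.28**

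| | mp-MRI | bp-MRI | bp − mp |
|---|---|---|---|
| All men | 0.76 × 0.28 = 21.28% | 0.74 × 0.28 = 20.72% | −0.56 points |
| MRI-positive share | 0.2128 + 0.11 × 0.72 = 29.20% | 0.2072 + 0.10 × 0.72 = 27.92% | |
| MRI-positive men only | 0.2128 / 0.2920 = 72.88% | 0.2072 / 0.2792 = 74.21% | +1.34 points |

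At D = 0.40 the differences are −0.80 and +0.98 points. MRI-positive men at 148 per arm: 148 × 0.2920 = 43 and 148 × 0.2792 = 41, so about 84 of 296 would remain.

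**Precision.** The 95% half-width is 1.96 × √(p₁(1 − p₁)/n₁ + p₂(1 − p₂)/n₂). At D = 0.28 it is 9.3 points over all men and 18.8 points over MRI-positive men. At D = 0.40 the two are 10.4 and 14.3 points. Each expected difference is less than a tenth of its half-width.

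**What the sign change rests on.** Over MRI-positive men, bp-MRI looks better only if its sens/(1 − spec) exceeds 0.76/0.11 = 6.91. With sensitivity 0.74 that needs specificity above 1 − 0.74/6.91 = 0.893. The cited value is 0.90. At 0.89, the mp-MRI value, the difference at D = 0.28 is 0.2072/0.2864 − 0.7288 = −0.5 points, and both readings agree in sign.

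**How often the signs differ by chance.** In 1,000,000 simulated trials per row at 148 per arm, the two point estimates had opposite signs as follows:

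| D, hit rate | Cited accuracies | Identical arms (76%/89% in both) |
|---|---|---|
| 0.28, 1.0 | 28.6% | 27.2% |
| 0.28, 0.8 | 23.0% | 22.0% |
| 0.40, 1.0 | 32.0% | 30.6% |
| 0.40, 0.8 | 24.7% | 23.8% |

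The cited difference between the MRIs adds about 1 to 1.5 points. The rest is sampling noise.

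**What the text favours**
1. The parent item counts men, in the same form as the primary endpoint and secondary endpoints 1 and 2, which cover all men.
2. Where a different base is meant, the plan names it, as in the per-lesion endpoint.
3. An MRI-negative man with 12 systematic cores has had the biopsy that section 4.1 schedules for him. Nothing planned is absent, so the missing-data rules have nothing to act on. If they did, section 11.4 would remove him from the study, and so from the primary analysis too, which nobody would intend.

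**Exclusive or inclusive.** Let T and S be the two reported counts and A the any-core count over the same men. If both lines are inclusive, T + S ≥ A and the overlap is T + S − A. If both are exclusive, T + S ≤ A and the overlap is A − T − S. If both lines follow the same convention, the three counts show which one was used and give back the full cross-table.

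**The case for a change.** The strongest case for acting is that the two readings are different quantities. The level moves from about 21% to about 73%, roughly 71-72% of each arm leaves the analysis, and the protection of randomisation is lost. None of that depends on the sign change. At the cited specificities, bp-MRI sensitivity could fall to 6.91 × 0.10 = 69.1% before the MRI-positive comparison showed any deficit. That is a loss of 1 − 0.691/0.76 = 9% of MRI-guided csPCa. The wording about men leans towards all men without saying so, and the section on analysis populations gives no help. A denominator chosen after seeing the data leaves room for selective reporting, and a sentence would cost almost nothing.

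What stands is that the denominator is not written down and that dropping MRI-negative men would be a poor analysis. It does not show that the plan leads there, because that takes a strained reading of the missing-data rule against the endpoint's own wording. The numerator is also the same count under both readings, so a report giving counts and denominators would show which was used. The synopsis also has an entry for the efficacy analysis group, listing intention-to-treat and per-protocol. The mark of choice cannot be read in the available text, so the entry in section 11.3 should not be taken as the plan's last word on populations.

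**Conclusion.** No change is needed. The missing denominator is a gap in detail on a descriptive secondary endpoint. Its natural reading, all men with MRI-negative men counted as not detected in targeted cores, is already the sound one. The alternative would matter for the level (about 73% instead of 21%) and would keep about 84 of 296 men, but the text does not call for it.

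The apparent reversal, −0.6 against +1.3 points, is a weak argument. It needs bp-MRI specificity above 0.893, lies within intervals of about ±9 and ±19 points, and shows up in simulation hardly more often than with identical arms. The figures assume that the cited overall accuracies apply to csPCa, that prevalence is 28%, and that targeting hits equally well in both arms.

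The meaning of exclusivity can be recovered from the reported counts. The title's wording is a matter of naming and changes no result. The primary endpoint, its test and its sample size do not depend on any of this.

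### A fixed block size of 4 at one hospital, with no allocation concealment described, leaves one third of allocations certain to anyone who knows the past assignments

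*Combined protocol and SAP*

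**What the plan says.** The randomisation is set out in section 4 (Study Design), before 4.1. The ratio is equal: "Patients will be randomized in a 1:1 manner to bp-MRI and mp-MRI". The planned total comes first ("we first plan to recruit a total of 370 participants"), and then the method: "we choose a block size of 4 to maintain balance between groups while reducing the predictability of the assignment sequence". A complete table of codes is generated in advance. As men enter, "they will be assigned to the respective groups according to the sequence of the random code table". The section closes by saying "After each assignment, we record the detailed information of the participants and the group they are assigned to", and gives traceability and transparency as the purpose.

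The trial has one site. The title page lists "Chang Gung Memorial Hospital at Linkou", and the synopsis gives this centre's planned enrolment as "本中心預計納入人數 370", equal to the whole-trial total.

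The section gives no second block size, stratification, holder of the table or concealment method. It does not say at what point relative to consent and eligibility the next code is released, and the schedule of activities has no row for randomisation.

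**The concern.** With every block of size 4, the fourth man's arm is always determined by the first three. The third man's arm is determined too whenever the first two went the same way. All 370 men come from one sequence at one hospital, so a single team could in principle follow it.

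The setting leaves room to act on that knowledge. PSA, rectal examination and ultrasound are done at screening, before the MRI, so markers of risk for clinically significant cancer (csPCa) are known early. The synopsis expects only 40–50% of men to agree, which leaves latitude over who is approached and when. The primary endpoint is the proportion with csPCa, so a difference in underlying prevalence between the arms would enter the non-inferiority comparison directly. No adjusted primary analysis is specified that might reduce it.

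**Working it through.** The documents state no figure for predictability, so there is none to reproduce. The inputs from section 4 and the synopsis are: block size 4, ratio 1:1, 370 men, one site. The margin of 10 points (section 11.1) is used only for scale.

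**Fixed blocks of 4.** There are 6 balanced orderings. The observer knows the block size and all past assignments.

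- Certain allocations per block: position 4 always, and position 3 when positions 1 and 2 match (2 of 6 orderings). (1 + 1/3)/4 = 33.3%.
- Over the trial: 370 = 92 × 4 + 2. The last two places are never certain, so 92 × 4/3 = 122.7 men, or 33.2% of 370.
- Best guess (the arm that is behind, a coin toss when level): (1/2 + 2/3 + 2/3 + 1)/4 = 17/24 = 70.8%. No information would give 50%.

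**Alternatives.** Fixed sizes were enumerated exactly. Randomly varying sizes were simulated (300 lists of 370) with an observer who knows the possible sizes and past assignments and updates by Bayes' rule.

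| Block sizes | Certain | Best guess right |
|---|---|---|
| Fixed 2 | 50% | 75% |
| **Fixed 4 (plan)** | **33.3%** | **70.8%** |
| Fixed 6 | 25% | 68.3% |
| Fixed 8 | 20% | 66.6% |
| Random 2, 4 | 11.2% | 72.2% |
| Random 2, 4, 6 | 4.3% | 70.3% |
| Random 4, 6 | 5.4% | 69.3% |
| Random 4, 8 | 7.6% | 67.9% |
| Random 4, 6, 8 | 2.1% | 68.0% |
| Random 6, 8, 10 | 1.5% | 66.5% |

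With random 4, 6 and 8, certain knowledge almost disappears. The excess of the best guess over 50% falls only from 20.8 to 18.0 points, about one seventh. Guessing the arm with fewer men so far, which needs no knowledge of the sizes, was right 68.1% of the time. Hiding the sizes therefore protects against certainty, but hardly against guessing.

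**Possible bias.** Let d be the difference in csPCa risk between men steered to one arm and men steered to the other. The documents give no value, so d = 5–10 points is an assumption. Every opportunity is taken to be used, always in the same direction, so the results are upper bounds for that d.

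- Acting only on certain allocations: bias = share certain × d. Fixed 4: 0.333 × 5 to 0.333 × 10 = 1.7–3.3 points. Random 4, 6, 8: 0.021 × 5 to 0.021 × 10 = 0.1–0.2 points.
- Acting on every guess: bias = (2g − 1) × d, where g is the share guessed right. Fixed 4: (2 × 0.708 − 1) = 0.417, giving 2.1–4.2 points. Random 4, 6, 8: (2 × 0.680 − 1) = 0.36, giving 1.8–3.6 points.

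**Final balance.** With fixed 4, the last two men fall in the same arm with probability 1/3 (2 of 6 orderings), giving 186:184. With sizes up to 8, an incomplete last block could leave a difference of at most 4 men (four in a row to one arm: 187:183).

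**The case against.** The strongest reply is that block size matters only if someone who recruits can follow past assignments, and the documents do not say so. That stands. A reader might infer from the closing sentence on recording that the arms are logged openly. The text says only that a record is made, as any trial would, and not who can see it. Nor does it say whether recruiters hold the protocol that gives the block size.

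The arms differ in the contrast sequence, so imaging staff can tell them apart, but no section says that those staff obtain consent. The scan may also come too late to help: the schedule puts it on Days 15–28, after registration on Days 1–14. At the expected 200–250 men a year (200/52 = 3.8 to 250/52 = 4.8 a week), a block fills in about a week. The synopsis blinding entry is a tick-box whose mark does not survive in the text available, so nothing rests on it.

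A second reply is that a block of 4 does reduce predictability compared with a block of 2 (33% against 50% certain). That also stands. A reader might call the choice contrary to its stated aim, but the plan names no comparator, so the statement is weak and not false.

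A third is that varying blocks barely help against someone who acts on every guess. The figures bear this out, and it limits what that change alone can claim. It does not remove the gain against certain knowledge, or the need to describe concealment.

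**Conclusion.** The point holds in a limited form and is worth correcting. The plan fixes one block size, prints it in the protocol, uses one sequence at one hospital, and describes no concealment. For an observer of past assignments, one third of allocations are certain and the best guess is right 70.8% of the time. That serves the aim of lower predictability poorly, when a set such as 4, 6 and 8 brings certain allocations to about 2%.

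Two stronger conclusions are not supported. Selection bias is not shown: it requires recruiters who see past assignments and act on them, which the documents neither state nor exclude. Nor would varying blocks largely remove such bias. They nearly eliminate certainty, but lower best-guess success only to 68%.

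The possible bias, at most 1.7–3.3 points (certain allocations only) or 2.1–4.2 points (every guess) against a 10-point margin, rests on the assumed 5–10 point difference and on full, one-directional exploitation. The predictability percentages do not depend on that assumption.

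**What to change.** For the list, or its unused part if enrolment has begun:

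1. In section 4, replace the single block size with randomly varying sizes such as 4, 6 and 8. Do not use 2 and 4, which raises best-guess success to 72%. The protocol need say only that sizes vary; the sizes can go in a restricted document.
2. State that the sizes and the code table are kept away from recruiting staff, and name by role an independent holder of the table.
3. State that each assignment is released only after consent and eligibility are recorded.

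Item 1 alone is not enough, and does nothing if recruiters can see the table. Items 2 and 3 carry most of the protection against guessing, provided recruiters also cannot see the record of past assignments.

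The cost is a regenerated list, a short amendment and a possible final imbalance of a few men. Exact 185:185 is not guaranteed under the present plan either, because 370 is not a multiple of 4.
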